5.5. Duration of therapy

Patients will receive protocol therapy unless:

- Patient withdraws consent.
- Patient has progression of disease as defined in section 7.0.
- Patient experiences unacceptable drug toxicity.

Duration of Follow-up

For this protocol, all patients, including those who discontinue protocol therapy early, will be followed until 1 month after discontinuation of therapy for metastatic disease. Date of last follow up clinic visit should be within 30 days of end of treatment (+/- 10 days).

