2.3. Secondary Objectives

- To assess ctDNA *ESR1* mutant allele fraction (MAF) and kinetics with fulvestrant compared with AI
- To assess the prevalence of *ESR1* mutations in patients with secondary resistance to endocrine therapy
- To correlate ctDNA with CA 15-3 tumor marker changes
- To assess overall survival (OS) with transition to fulvestrant compared with continuing AI therapy in patients with emergence of *ESR1* mutations
- To assess PFS and time to next treatment (TTNT) on next line of therapy after progression on fulvestrant vs. AI in combination with CDKI

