4.2. Instructions for patients who do not start assigned protocol treatment

If a patient does not receive any assigned protocol treatment, baseline and follow-up data will still be collected. Document the reason for not starting protocol treatment on one of the baseline forms. Also report the date and type of the first non-protocol treatment that the patient receives.

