5.3. Concomitant Therapy

Patients must be instructed not to take any medications (over-the-counter or other products) during the protocol treatment period without prior consultation with the investigator. All medications (other than study drug) taken within 28 days of starting study treatment through the 30-day safety follow up visit should be reported on the CRF.

All supportive measures consistent with optimal patient care should be given throughout the study. Exceptions include the use of growth factors to treat anemia or thrombocytopenia as such use has been associated with decreased survival and increased thrombotic events in patients with breast cancer. The use of myeloid growth factors in the form of G-CSF should follow ASCO guidelines. G-CSF can be administered to treat CDK inhibitor-induced neutropenia as determined by the treating physician.

Dose Modifications for Use with Strong CYP3A Inhibitors

Concomitant use of strong CYP3A inhibitors should be avoided with **palbociclib**. If patients must be co-administered with a strong CYP3A inhibitor, dose of Palbociclib should be reduced to 75 mg daily. Avoid concurrent use of palbociclib with strong CYP3A inducers. The dose of sensitive CYP3A4 substrates with narrow therapeutic indices may need to be reduced when given concurrently with palbociclib.

Concomitant use of strong CYP3A inhibitors should be avoided with **ribociclib**. If patients must be co-administered with a strong CYP3A inhibitor, dose of ribociclib should be reduced to 400 mg daily. Avoid

concomitant use of ribociclib with strong CYP3A inducers. The dose of sensitive CYP3A4 substrates with narrow therapeutic indices may need to be reduced when given concurrently with ribociclib.

Concomitant use of ketoconazole should be avoided with **abemaciclib**. If patients must the co-administered with a strong CYP3A inhibitor, dose of abemaciclib should be reduced to 100 mg twice daily. Avoid concomitant use of abemaciclib with strong CYP3A inducers.

Patients should avoid pomegranates or pomegranate juice, grapefruit, all of which are known to inhibit cytochrome CYP3A enzymes and may increase the exposure to palbociclib and ribociclib.

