9. STATISTICAL CONSIDERATIONS

Primary/Secondary Objectives:

This is a randomized, open-label, Phase II, for HR positive advanced breast cancer patients who have been treated with AI and CDK as first line in the metastatic setting for at least 12 months and who have *ESR1* mutations identified through ctDNA assay.

[name], MS, Department of Biostatistics at MD Anderson Cancer Center, will oversee the implementation of the statistical analysis. The primary endpoint is PFS, which is measured from the date of study randomization to the date of event (ie, death and/or disease progression) or the date of last follow-up if no event has occurred. Survival curves for PFS will be analyzed using the Kaplan-Meier method and survival difference across groups will be examined by log rank test. Patients alive and disease-free at the latest clinical evaluation will be censored for PFS at the date of that evaluation. We will estimate the treatment comparison with 95% confidence intervals and p-value using Cox proportional hazards regression and we will assess the proportional hazard assumption using graphs of rescaled Schoenfeld residuals and related tests. We would attempt to identify independent predictors of PFS using multivariable Cox PH regression analysis. Analysis for OS and PFS from the start of next line of therapy will be performed as described for PFS from the date of randomization. Randomization will be performed using Core. Stratification factors include recurrence free interval (\leq 3 years vs. $>$ 3 years), prior adjuvant endocrine therapy (tamoxifen vs. aromatase inhibitor), and site of metastasis (bone vs. visceral).

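### OS, next-line PFS and TTNT are planned, but no outcome collection is stated beyond about 30 days after treatment for patients who start it, and the next-line PFS comparison is not protected by randomisation

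*Combined protocol and SAP*

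**What the plan says.** **Endpoints.** Sections 2.3 and 2.4 list OS, PFS and TTNT. One objective is "To assess PFS and time to next treatment (TTNT) on next line of therapy after progression on fulvestrant vs. AI in combination with CDKI". Section 9 adds: "Analysis for OS and PFS from the start of next line of therapy will be performed as described for PFS from the date of randomization". The method it refers to is Kaplan-Meier curves with a Cox model, where "survival difference across groups will be examined by log rank test".

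**End of follow-up (Section 5.5).** The first sentence says that "all patients, including those who discontinue protocol therapy early, will be followed until 1 month after discontinuation of therapy for metastatic disease". The second says: "Date of last follow up clinic visit should be within 30 days of end of treatment (+/- 10 days").

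**What is collected, and until when, in patients who start treatment.**
- Medications other than study drug (Section 5.3, Appendix 1 note a): "through the 30-day safety follow up visit should be reported on the CRF".
- Serious adverse events, which include death (Section 5.4): to 30 days after the last dose.
- Imaging: to progression (Section 6.2) or the 30-day visit (Section 7.1).
- Appendix 1: the last column is the end-of-treatment or progression visit.

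**Patients who never start (Section 4.2).** Follow-up data are still collected, with the instruction "Also report the date and type of the first non-protocol treatment that the patient receives". No matching instruction is given for patients who do start.

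**The concern.** There are two separate problems.

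1. **Data.** Three planned endpoints depend on events after first progression. The stated collection windows close at progression or about a month after treatment, and the follow-up paragraph can be read either way. Section 1.2 hypothesises that early intervention improves survival. OS and outcomes through the next line help to show whether early switching adds benefit or only brings fulvestrant forward. Vital status not collected as the trial runs may be hard to recover, since Section 5.1 lets patients be treated elsewhere.

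2. **Comparison.** Only patients who progressed and began a new therapy have a next-line start date. A log rank or Cox comparison from that date is conditional on something that happens after randomisation and that treatment is expected to change. A difference could reflect who reached the next line, and when, rather than the effect of the assigned arm.

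Two definitions are also loose. Section 9 names no analysis for TTNT, and its sentence on OS and next-line PFS can be read as giving OS either time origin.

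**Working it through.** **Inputs from Section 9.** 124 patients, median PFS 5 (AI) and 9 (fulvestrant) months, 4-5 patients per month, 5 months' follow-up after accrual, two-sided 5%, 84 expected PFS events. **Assumed:** 1:1 allocation (62 per arm), uniform accrual, exponential PFS, no dropout.

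**Step 1. The plan's power.** With λ = ln 2/median, accrual time A and follow-up F, the chance of a PFS event by the end is

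p = 1 − [exp(−λF) − exp(−λ(A+F))]/(λA).

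At 5 per month (A = 24.8), p is 0.859 and 0.697, giving 62 × (0.859 + 0.697) = 96.5 events. Power is Φ(ln(9/5) × √(96.5/4) − 1.96) = Φ(0.93) = 82%, against 81% in the plan's table, so the model matches the plan closely. The same inputs give 96-101 events over 4-5 per month, not 84, so both cut-offs are used below.

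**Step 2. Who could enter the next-line comparison.** Share with a PFS event:

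| Cut-off | AI | Fulvestrant |
|---|---|---|
| 84 events (4.5 per month) | 76% (47 of 62) | 60% (37 of 62) |
| End of planned follow-up (4-5 per month) | 86-89% | 70-74% |

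These are upper limits on entry, because deaths without progression and patients given no further therapy drop out. Under the plan's own alternative, entry differs by arm by about 15 points.

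**Step 3. Deaths seen on the shorter reading of Section 5.5.** The documents give no OS for this population. As an assumption, median OS from randomisation is set to 20 and 26 months in both arms. These are the ESR1-mutant OS figures in Section 1.1, from another trial. With exponential survival after progression at rate μ,

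S(t) = [μ exp(−λt) − λ exp(−μt)]/(μ − λ),

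and μ is solved so that S(M) = 0.5. Median survival after progression is then 12.2 (AI) and 7.5 (fulvestrant) months for M = 20, and 18.1 and 12.6 for M = 26. A death counts as seen if it falls within 30-40 days of progression, which is the 30 days plus the 10-day allowance. No deaths before progression are assumed.

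Hand check for M = 20, 30 days (0.986 month), end of follow-up at 4.5 per month:
- AI: 54.1 × (1 − 2^(−0.986/12.2)) = 2.9
- Fulvestrant: 44.5 × (1 − 2^(−0.986/7.5)) = 3.9
- The sum is 6.8, or 6.7 once deaths after the cut-off are removed.

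| Cut-off | Deaths seen | Deaths with full follow-up |
|---|---|---|
| 84 PFS events (4-5 per month) | 3.6-7.4 | 29-43 |
| End of planned follow-up (4.5 per month) | 4.3-8.8 | 42-55 |

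If 5-10% of PFS events are deaths (assumed), the number seen at the end of planned follow-up rises to about 9-17.

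**Step 4. What this does to an OS hazard ratio.** The 95% CI is the estimate divided and multiplied by exp(1.96 × 2/√d), where d is the number of deaths. At the end of planned follow-up:
- d = 4.3 gives 6.6 and d = 8.8 gives 3.7 (the normal approximation is poor at so few deaths).
- d = 42 gives 1.83 and d = 55 gives 1.70.

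**Step 5. The longer reading.** If 10-50% of deaths fall after the 1-month tail (assumed), between 42 × 0.5 = 21 and 55 × 0.9 = 49.5 deaths are seen. The factors are 2.35 and 1.75.

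**Step 6. Next-line progressions on the shorter reading.** Next-line medians of 4.6-9.5 months are assumed (the PALOMA-3 arms in Section 1.3), with the next line starting 0-0.5 months after progression. About 3-18 progressions fall inside the window, against about 51-80 by the end of planned follow-up.

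**The case against.** **Early events are caught.** A reader might infer that nothing about next therapy or death is recorded once treatment ends. The documents do not support that. Sections 5.3 and 5.4 capture medications and deaths for about 30 days. If the next line starts within two weeks of progression, its start date would usually fall inside that window, so first next therapy is partly covered. Later therapy, next-line progression and later vital status are not.

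**The longer reading is credible.** A reader might infer that follow-up definitely stops one month after protocol therapy. That goes too far. The first sentence of Section 5.5 contrasts protocol therapy with therapy for metastatic disease, which favours follow-up through later lines, and the second dates only a clinic visit. Section 4.2 also implies that follow-up is the default. This stands, and it makes the shorter-reading figures a worst case. It still supplies no visit, contact or form.

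**OS censoring.** A reader might infer that OS would be censored at the last clinical evaluation, because Section 9 says "Patients alive and disease-free at the latest clinical evaluation will be censored for PFS at the date of that evaluation". That rule is for PFS in disease-free patients. The general rule in Section 9, censoring at last follow-up when no event has occurred, carries over to OS more naturally. What remains is that the last follow-up date depends on how Section 5.5 is read.

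**The death counts are illustrative.** The OS medians come from another trial, and forcing equal medians in both arms makes post-progression survival shorter on fulvestrant. That is fair. With post-progression medians of 12, 20 and 30 months in both arms instead, about 5, 3 and 2 deaths are seen within a month, out of 49, 35 and 26. That is again about a tenth.

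**These are secondary endpoints in a phase II trial.** True, and it limits the weight of the point. The objective's wording could also give TTNT the same origin as next-line PFS, and PFS2 would be a new endpoint. But Section 9 does specify a between-arm test from next-line start, and calling it secondary does not make the two groups comparable.

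**Conclusion.** The point holds, as one that should be fixed. For patients who start treatment, the protocol plans OS, next-line PFS and TTNT without stating how vital status, later therapy or next-line progression is obtained beyond about 30 days after treatment, and Section 5.5 is ambiguous on when follow-up ends.

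The size depends on the reading. On the shorter one, most deaths and most next-line progressions would be missed and OS would be close to uninformative. On the longer one, the loss is smaller but collection is still unspecified. The death and next-line counts rest on medians borrowed from other trials. The entry percentages rest only on the plan's medians and accrual, with the assumptions listed.

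The between-arm comparison of PFS from next-line start is not protected by randomisation on either reading.

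A reader might infer that the main result is at risk. It is not, because primary PFS runs from randomisation to first progression or death and imaging continues until progression. Confidence is moderate: the CRFs are not in the documents and may contain fields that the protocol does not mention.

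**What to change.** 1. Reconcile the two sentences in Section 5.5 with each other and with Sections 2.3, 6.2, 7.1, 9 and Appendix 1, by separating the 30-day safety window from outcome follow-up.
2. After treatment ends, collect vital status, date and type of next therapy, and the next progression date as recorded in routine care. Do this by chart review or telephone until death, withdrawal or study close, and add a matching column to Appendix 1.
3. State that OS runs from randomisation in all randomised patients and is censored at the date last known alive.
4. State the time origin for TTNT, using randomisation for any between-arm comparison.
5. Add PFS2 (randomisation to progression on the next line, or death) as the between-arm comparison, and report PFS from next-line start as descriptive only. That keeps the Section 2.3 question without a causal claim.

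**Cost.** A protocol amendment and modest periodic follow-up of about 124 patients. Next-line progression dates from routine care will be less standardised than on-study PFS, because study imaging stops at progression and treatment may be local. Vital status and next-therapy dates do not share that weakness. The primary analysis does not change.

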6. SCHEDULED EVALUATIONS

6.1. Pre-treatment evaluation

Baseline laboratory assessments should be performed as per standard of care for palbociclib, ribociclib, abemaciclib, and fulvestrant. Schedule of clinical assessments is listed in **Appendix 1**

- History and physical examination.
- Radiologic evaluation within 4 weeks prior to Cycle 1.
- Patient must sign IRB-approved informed consent prior to any study-specific procedures unless such procedures are part of the standard of care.
- Screening ctDNA Blood draw: Guardant360 StreckTM cell preservation tubes (8-10 mL x 2 per blood draw).

6.2. Evaluation during study

Follow up laboratory assessments should be performed as per standard of care for palbociclib, ribociclib, abemaciclib, and fulvestrant

- Physical examination (including vital signs, weight, performance status)
- Patients will undergo restaging with complete imaging (CT CAP and bone scan) approximately every 3-4 cycles of therapy for the first 12 months and every 3-6 months thereafter until progression.
- Exploratory ctDNA blood draws (Guardant360 StreckTM cell preservation tubes (8-10 mL x 2 per blood draw) will be performed at Cycle 2, Cycle 4 and Cycle 12. These will be banked at MDACC. ctDNA will be drawn on the same date as standard of care labs assessments.
- End of Treatment/Progression ctDNA Blood draw (Guardant360 StreckTM cell preservation tubes (8-10 mL x 2 per blood draw).

6.3. Pregnancy and assessments of fertility

Based on animal studies, CDK inhibitors can potentially cause fetal harm when administered to pregnant women. In animal reproduction studies, administration of CDK inhibitors during organogenesis resulted in embryo-fetal toxicity.

Women of child-bearing potential, defined as all women physiologically capable of becoming pregnant, must use highly effective contraception during the study and for at least 4 weeks after stopping treatment. Highly effective contraception is defined as either:

- Total abstinence: When this is in line with the preferred and usual lifestyle of the subject. [Periodic abstinence (e.g., calendar, ovulation, symptothermal, post-ovulation methods) and withdrawal are not acceptable methods of contraception].
- Sterilization: have had surgical bilateral oophorectomy (with or without hysterectomy) or tubal ligation at least six weeks before taking study treatment. In case of oophorectomy alone, only when the reproductive status of the woman has been confirmed by follow up hormone level assessment.
- Male partner sterilization (with the appropriate post-vasectomy documentation of the absence of sperm in the ejaculate).
- Use of a combination of the following
 - a. Placement of an intrauterine device (IUD) or intrauterine system (IUS).

Proprietary of MD Anderson Cancer Center

Protocol 2018-0287

January 8, 2020

- b. Barrier methods of contraception: Condom or Occlusive cap (diaphragm or cervical/vault caps) with spermicidal foam/gel/film/cream/vaginal suppository.

Male Contraception

- Sexually active males must use a condom during intercourse while taking the drug and for 4 weeks after stopping treatment and should not father a child in this period.
- A condom is required to be used also by vasectomized men in order to prevent delivery of the drug via seminal fluid.
- Female partners of male patients must also be advised to use one of the following contraception methods: Use of (1) oral, injected, implanted or other hormonal methods of contraception, or (2) intrauterine device (IUD) or intrauterine system (IUS), or (3) prior male/female sterilization.

7. MEASUREMENT OF EFFECT

7.1. RECIST Criteria in metastatic disease

Tumor response for patients with measurable lesions should be assessed using RECIST 1.1[32]. Patients with measurable lesions should be assessed using contrast-enhanced CT of the chest, abdomen and/or MRI scan of the chest, abdomen and pelvis approximately (+/- 7 days) every three cycles (cycle length is 28 days), from the date of first dose of fulvestrant until the 30-day follow-up visit. Although progression may be determined by the investigator based upon clinical deterioration, every effort should be made to document progression using radiographic methods. The basis for determination of progression per clinical deterioration should be documented.

Note: It is very important that the same method of radiologic assessment be used throughout the study and that the same lesions are followed.

Response Criteria

Changes in the largest diameter of the tumor lesions and the shortest diameter in the case of malignant lymph nodes should be used in RECIST assessment.

Complete Response (CR): Disappearance of all target lesions. Any pathological lymph nodes (whether target or non-target) must have reduction in short axis to <10 mm.

Partial Response (PR): At least a 30% decrease in the sum of the diameters of target lesions, taking as reference the baseline sum diameters.

Progressive Disease (PD): At least a 20% increase in the sum of the diameters of target lesions, taking as reference the smallest sum on study (this includes the baseline sum if that is the smallest on study). In addition to the relative increase of 20%, the sum must also demonstrate an absolute increase of at least 5 mm. (Note: the appearance of one or more new lesions is also considered progressions).

Stable Disease (SD): Neither sufficient shrinkage to qualify for PR nor sufficient increase to qualify for PD, taking as reference the smallest sum diameters while on study.

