8. BIOMARKER AND CORRELATIVE STUDIES

ctDNA analysis

To identify *ESR1* alterations, patients will have mandatory ctDNA assessment prior to randomization. In addition, to assess mutant allele fraction/ somatic allele burden (SAB) plasma for ctDNA would be obtained at 4, 12 weeks, and at progression. Blood draw for ctDNA would be stored in Guardant360 StreckTM cell preservation tubes (8-10 mL x 2 per blood draw). Where possible, blood samples for ctDNA will be drawn from patients scheduled to have venipuncture for standard of care labs assessments for clinical care. Patients with activating *ESR1* mutations will be treated until radiological disease progression. To characterize candidate mechanisms of resistance, Guardant 360 ctDNA analyses will be performed at disease progression and compared with pre-treatment ctDNA analyses. Specifically, we will evaluate alterations in *TP53* and *PIK3CA* and correlate with PFS. We will also evaluate for acquired *RB* mutations as well as other emergent genomic alterations with exposure to CDK inhibitors. We will correlate ctDNA dynamics with changes in CA 15-3 tumor marker. We will also correlate ctDNA dynamics and velocity with responses seen on imaging.

Solid Tumor Genomic Assay 2018									
Hotspot Genes				Full-Length		Copy Number		Gene Fusions	
n = 87				n = 48		n = 47		n = 51	
AKT1	FGFR1	MAP2K1	RAF1	ARID1A	NOTCH3	AKT1	IGF1R	AKT2	MYBL1
AKT2	FGFR2	MAP2K2	RET	ATM	PALB2	AKT2	KIT	ALK	NF1
AKT3	FGFR3	MAP2K4	RHEB	ATR	PIK3R1	AKT3	KRAS	AR	NOTCH1
ALK	FGFR4	MAPK1	RHOA	ATRX	PMS2	ALK	MDM2	AXL	NOTCH4
AR	FLT3	MAX	ROS1	BAP1	POLE	AR	MDM4	BRAF	NRG1
ARAF	FOXL2	MDM4	SF3B1	BRCA1	PTCH1	AXL	MET	BRCA1	NTRK1
AXL	GATA2	MED12	SMAD4	BRCA2	PTEN	BRAF	MYC	BRCA2	NTRK2
BRAF	GNA11	MET	SMO	CDK12	RAD50	CCND1	MYCL	CDKN2A	NTRK3
BTK	GNAQ	MTOR	SPOP	CDKN1B	RAD51	CCND2	MYCN	EGFR	NUTM1
CBL	GNAS	MYC	SRC	CDKN2A	RAD51B	CCND3	NTRK1	ERBB2	PDGFRA
CCND1	H3F3A	MYCN	STAT3	CDKN2B	RAD51C	CCNE1	NTRK2	ERBB4	PDGFRB
CDK4	HIST1H3B	MYD88	TERT	CHEK1	RAD51D	CDK2	NTRK3	ERG	PIK3CA
CDK6	HNF1A	NFE2L2	TOP1	CREBBP	RB1	CDK4	PDGFRA	ESR1	PPARG
CHEK2	HRAS	NRAS	U2AF1	FANCA	RNF43	CDK6	PDGFRB	ETV1	PRKACA
CSF1R	IDH1	NTRK1	XPO1	FANCD2	SETD2	CDKN2A	PIK3CA	ETV4	PRKACB
CTNNB1	IDH2	NTRK2		FANCI	SLX4	CDKN2B	PIK3CB	ETV5	PTEN
DDR2	JAK1	NTRK3		FBXW7	SMARCA4	EGFR	PPARG	FGFR1	RAD51B
EGFR	JAK2	PDGFR		MLH1	SMARCB1	ERBB2	RICTOR	FGFR2	RAF1
ERBB2	JAK3	PDGFRB		MRE11A	STK11	ESR1	TERT	FGFR3	RB1
ERBB3	KDR	PIK3CA		MSH2	TP53	FGF19	TSC1	FGR	RELA
ERBB4	KIT	PIK3CB		MSH6	TSC1	FGF3	TSC2	FLT3	RET

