Appendix 1 Schedule of clinical assessments

Evaluation	Screening	Cycle 1	Cycle 2	Cycle 4	Cycle 12	End of treatment/ Progression
Physical exam, Vital Signs	X ^a					
ECOG PS	X ^a					
Hematology and Chemistry	Z					
Coagulation (PT/PTT/INR)	Z					
Pregnancy Test (urine)*	X					
Liquid Biopsy **	X**		X***	X***	X***	X**
Concomitant medications	X ^a					
Fulvestrant^d administration		X	X	X	X	
Imaging	X ^b			X	X	X
Tumor marker	X		X	X ^c	X	

* For women of child bearing age. Repeated at the discretion of treating physician

^zLabs and clinical monitoring should be performed as per standard of care for CDK4/6 with AI/fulvestrant use

^{**} Guardant ctDNA assessments are collected at screening (for baseline *ESR1* assessment), at progression.

^{***}Exploratory samples for ctDNA assessment will be collected at Cycle 2, Cycle 4 and Cycle 12 and will be banked at MDACC and processed at Guardant Health at the time of study conclusion.

^a All medications (other than study drug) taken within 28 days of starting study treatment through the 30-day safety follow up visit should be reported on the CRF.

^b Tumor imaging (CT/Bone scan) will be performed approximately every 3-4 cycles of therapy for the first 12 months and every 3-6 months thereafter until progression. Tumor imaging should be performed at MD Anderson.

^c Tumor markers (CA 15-3) performed approximately every 3 cycles (12 weeks) until disease progression in coordination with routine labs and imaging

^d Fulvestrant administration for patients randomized to the fulvestrant arm only (+/- 7 days). Second dose of fulvestrant to be administered at C1D15. Control patients would continue the treatment they were already on (CDK inhibitor in combination with aromatase inhibitors). Fulvestrant can be administered under the supervision of treating physician locally.

Proprietary of MD Anderson Cancer Center

Protocol 2018-0287

January 8, 2020

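### Section 7.1 times scans from a first fulvestrant dose that controls never receive, and it conflicts with Section 6.2 and Appendix 1; PFS needs one scan calendar for both arms, counted from randomisation

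*Combined protocol and SAP*

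**What the plan says.** Section 7.1 covers patients with measurable lesions in either arm. It schedules scans "approximately (+/- 7 days) every three cycles (cycle length is 28 days"), counted "from the date of first dose of fulvestrant until the 30-day follow-up visit". It prefers radiographic documentation but leaves another route: "Although progression may be determined by the investigator based upon clinical deterioration".

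Section 6.2 covers all patients and schedules imaging "approximately every 3-4 cycles of therapy for the first 12 months and every 3-6 months thereafter until progression". Note b of Appendix 1 repeats this, and the Appendix 1 grid marks imaging at screening, Cycle 4, Cycle 12 and end of treatment or progression.

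On who is treated with what, Appendix 1 has "Fulvestrant administration for patients randomized to the fulvestrant arm only (+/- 7 days") and, for the other arm, "Control patients would continue the treatment they were already on". Section 9 measures PFS from randomisation in both arms and censors event-free patients at their latest clinical evaluation. No passage says which imaging rule governs.

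**The concern.** A stated rule for timing the primary endpoint cannot be applied to one arm. Controls have no first fulvestrant dose under the protocol. Nor does a patient randomised to fulvestrant who never starts it, although Section 4.2 keeps that patient in follow-up. A reader could apply 7.1 to the fulvestrant arm and 6.2 to controls, or could scan everyone every 84 days but start the clock at first dose in one arm and at randomisation in the other.

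Progression is dated mainly by scans, and the trial is open-label. If scan timing differs by arm, recorded PFS differs by arm even when the treatments are equivalent. The schedule is coarse relative to the assumed control median of 5 months, so a small shift in timing can reorder many events.

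**Working it through.** **1. The two rules compared**

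| | Section 7.1 | Section 6.2 and Appendix 1 |
|---|---|---|
| Who | measurable lesions, either arm | all patients |
| Origin | first fulvestrant dose | study cycle; Day 1 of Cycle 1 not defined for controls |
| Year one | 3 × 28 = 84 days (77-91 with the window) | 3-4 cycles = 84-112 days |
| After month 12 | still 84 days (77-91) | 3-6 months, about 91-183 days |
| Stop | 30-day follow-up visit | progression |

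In year one the rules meet at the 3-cycle option; 4 cycles (112 days) lies outside 77-91. After month 12 they meet only near 91 days.

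Section 6.2 says banked ctDNA draws "will be performed at Cycle 2, Cycle 4 and Cycle 12", while Section 8 has "plasma for ctDNA would be obtained at 4, 12 weeks, and at progression". Read together, these put Cycle 2 at week 4 and Cycle 4 at week 12, that is, at cycle start. On that reading Cycle 12 starts at 11 × 28 = day 308 (Cycle 1 Day 1 as day 0). A three-cycle calendar gives days 84, 168, 252 and 336, so the Cycle 12 scan falls off it.

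The stopping points differ only for patients who stop before progression, which Section 5.5 allows. Under 7.1 their scans end at the 30-day visit; under 6.2 they continue, so the censoring date under Section 9 can differ.

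**2. Coarseness.** The control median of 5 months is about 152 days. On a 12-week calendar the second scan is due no earlier than 168 - 7 = day 161, so only one scheduled scan falls before the median.

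**3. The plan's own power.** Section 9 gives medians of 5 and 9 months, 124 patients, accrual of 4-5 per month, 5 months of further follow-up, two-sided 5% and a log-rank test. Assuming 1:1 allocation, exponential PFS and no dropout, accrual takes 124/4.5 = 27.6 months and 98.6 events are expected. The Freedman form gives Φ(√98.6 × (1 - 5/9)/(1 + 5/9) - 1.96) = Φ(0.877) = 81%, matching the power table. The stated 84 events do not reproduce; that is a separate matter and is not used in the main runs.

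**4. Effect of unequal timing, by simulation.** Set-up: 62 patients per arm, exponential PFS, control median 5 months, accrual and follow-up as above, log-rank at |Z| > 1.96, no interim analysis. Progression is recorded at the next scan. The 84-day calendar has ±7 days of jitter. The 6.2 calendar draws 12-16 weeks for 12 months, then 3-6 months. The first two unequal rows below are upper bounds: every patient is measurable and all progression is found at scans. The nominal one-sided error is 2.5%.

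| Calendars | Null HR | False results |
|---|---|---|
| Same in both arms | 1.00 | 2-3% each way; power 78-80% |
| Fulvestrant on 7.1, 0-14 days late; controls on 6.2 | 1.08-1.15 | 6-11% against fulvestrant; power about 66% at no delay |
| Both every 84 days; fulvestrant clock 7-14 days late | 0.85-0.88 | 9-11% for fulvestrant |
| 50% measurable, 7 days late, controls on 6.2 | 1.06 | - |
| 50% measurable, 7 days late, controls every 84 days | 0.97 | 3-4% for fulvestrant |

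In the second row the null HR is about 1.15, 1.12 and 1.08 for delays of 0, 7 and 14 days. In the third row the false-result rate depends on how event-free patients are censored: at 14 days, a run covering censoring at last scan and at data cut-off gave HR 0.83-0.86 and 12-15%. Adding 20% clinically dated events to the last row gave HR 0.98 and 3%.

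**The case against.** The strongest reply is that controls are not without a schedule. Section 6.2 and Appendix 1 cover both arms, and Section 5.1 asks for staging scans at MD Anderson, which makes uniform practice more likely. Nothing says the arms will be scanned differently. All of this stands, and it limits the point to a conflict that must be reconciled, not evidence of a biased result.

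Three stronger readings are tempting, and the documents support none of them.

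- **That the wording favours fulvestrant.** This holds only if measurable controls are scanned every 84 days from randomisation, which no passage states. On the only stated rule that fits controls, the bias runs against fulvestrant.
- **That the dosing windows show a delay of 3-7 days.** The ±3 days in Section 5.1 and ±7 days in Appendix 1 are symmetric windows around dosing days. They do not measure the time from randomisation to first dose, which the documents do not give.
- **That controls, already on at least 12 months of therapy, are past the first 12 months and so on the sparser schedule.** The study-cycle grid in Appendix 1 points to study months, though the text should say so.

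The stopping-point conflict is also narrow. Section 5.5 follows patients until 1 month after therapy for metastatic disease ends, which may soften it if that phrase includes later lines.

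**Conclusion.** The conflict is real and touches the primary endpoint: the 7.1 origin does not exist for controls, and its interval and stopping point differ from those of 6.2 and Appendix 1. Bias arises only if scan timing differs by arm, and its direction cannot be told from the documents. The upper bounds are a null hazard ratio of about 1.08-1.15 or about 0.85-0.88. They rest on assumed delays, all patients measurable and all progression found at scans. With half the patients measurable and a 7-day delay they shrink to about 1.06 or 0.97. Under one calendar there is no bias, so the realistic effect may be small. The change should be made because it is cheap and removes a rule that one arm cannot follow. It does not call the sample size into question.

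**What to change.** Reconcile Sections 5.5, 6.1, 6.2 and 7.1 and Appendix 1 into one tumour-assessment calendar:

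- identical in both arms, for measurable and non-measurable disease;
- counted from randomisation, the PFS origin, and not shifted by dosing delays;
- with the first fulvestrant dose removed as the scan origin in 7.1;
- with Cycle 1 and the first 12 months given the same origin in both arms;
- with one interval and one stopping point, chosen by the sponsor from its own stated rules and applied equally to both arms.

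The cost is protocol wording, plus some additional standard scans if the sponsor keeps 84 days after month 12 (roughly double the number under the 6-month option) or keeps scanning until progression. Sample size and analysis method do not change.
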